The increase in serum phosphorus observed after treatment with pemigatinib was exposure-dependent and followed a sigmoid relationship. A population Emax model of pemigatinib AUC and maximal serum phosphate change from baseline was developed. For those participants treated with pemigatinib 13.5 mg who did not develop hyperphosphatemia, AUC for pemigatinib 18 mg was estimated using a linear exposure relationship. Maximal serum phosphate change from baseline for each individual was then estimated using a population model. The maximal serum phosphate after treatment with pemigatinib 18 mg was calculated by adding the baseline of serum phosphate. The simulation suggested that the serum phosphate would increase above 5.5 mg/dL after treatment with pemigatinib 18 mg for the participants treated with pemigatinib 13.5 mg who did not develop hyperphosphatemia.

Figure 2: Comparison of Steady State Exposures for Pemigatinib 13.5 mg QD Between Subjects With Nonhyperphosphatemia and Hyperphosphatemia

AUCss = area under the curve at steady state; Css, min = minimum blood plasma concentration at steady state; HP = hyperphosphatemia.

Any participant who does not reach the target serum phosphate level of  $> 5.5$  mg/dL at any time during Cycle 1, and who is compliant with taking study drug and does not experience an ongoing Grade 2 or higher treatment-related AEs, will increase the daily dose to 18 mg starting at Cycle 2 Day 1. Participants who are titrated up to 18 mg QD will begin the next cycle at the new dose level and must agree to all Cycle 1 assessments (PK and safety assessments [hematology and blood chemistry]). Up-titration may occur no earlier than on Day 1 of Cycle 2, so that participants are observed for phosphate level and AEs at least for 1 cycle.

For participants who are up-titrated from 13.5 mg to 18 mg, a maximum of 2 dose level reductions is also recommended: 18 mg can be decreased to 13.5 mg, and if additional dose reduction is required, participants can decrease to 9 mg. Dose reductions below 9 mg are not allowed."

[figure not shown]
A CYP3A4-mediated drug-drug interaction study (INCB 54828-104) indicated there is evidence of a clinically significant effect on pemigatinib exposure when co-administered with a potent CYP3A4 inhibitor, itraconazole (increased pemigatinib AUC by 88%) or

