#### 8.1 Dose Level Reductions (if needed for management of potential adverse event)

Dose Level	Pemigatinib
1	18 mg PO QD
0	13.5 mg PO QD
-1	9 mg PO QD

\* All patients are scheduled to initiate Pemigatinib at Dose Level 0.

See section 7.1 for dose escalation information.

Note: If dose escalated, please report as modified treatment in Rave.

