Any other Grade 3 toxicity, if clinically significant and not manageable by supportive care.	Pemigatinib	
Step 1: Hold/Delay Pemigatinib up to 2 weeks (14 days), until toxicity resolves to <math>\leq</math> Grade 1.
 
Step 2: If assessed by the investigator as not related or unlikely related to Pemigatinib, then restart Pemigatinib at same dose; monitor as clinically indicated.
 
Step 2: If assessed by the investigator as possibly, probably or definitely related to Pemigatinib, then restart Pemigatinib at the next lower dose level; monitor as clinically indicated.

Any recurrent Grade 3 toxicity after 2 dose reductions.	Pemigatinib	Permanently discontinue Pemigatinib and initiate post-treatment follow-up per Protocol. (Exceptions require written approval of sponsor-investigator.)

Any other Grade 4 toxicity, if clinically significant	Pemigatinib	Permanently discontinue Pemigatinib and initiate post-treatment follow-up per Protocol.
---	-------------	--

\* Located at [REDACTED]

\*\* The following describe actions in the Action column:

- Hold/Delay = Treatment can be made up (see Section 8.3) as part of this cycle;
- Discontinue = Treatment is totally stopped.

Hyperphosphatemia is an expected on-target pharmacologic effect of FGFR inhibition. Hyperphosphatemia should be managed with diet modifications, phosphate binders and diuretics, or a dose reduction per the recommendations in the below table:

Recommended Approach for Hyperphosphatemia Management			
Serum Phosphate Level	Supportive Care	Guidance for Interruption/Discontinuation of Pemigatinib	Guidance for Restarting Pemigatinib
> 5.5 mg/dL and $\leq$ 7 mg/dL	Initiate a low-phosphate diet.	No action.	Not applicable.

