> 7 mg/dL and $\leq$ 10 mg/dL	Initiate/continue a low-phosphate diet and initiate phosphate-binding therapy once serum phosphate level is > 7 mg/dL.  Monitor serum phosphate at least twice a week and adjust the dose of binders as needed; continue to monitor serum phosphate at least twice a week until return to normal range.	If serum phosphate level continues to be > 7 mg/dL and $\leq$ 10 mg/dL with concomitant phosphate-binding therapy for 2 weeks, or if there is recurrence of serum phosphate level in this range, hold/delay Pemigatinib for up to 2 weeks	Restart Pemigatinib at the same dose when serum phosphate is < 7 mg/dL.  If serum phosphate level recurs at > 7 mg/dL, restart Pemigatinib with dose reduction .

> 10 mg/dL	
Continue to maintain a low-phosphate diet, adjust phosphate-binding therapy, and start/continue phosphaturic agent.
 
Continue to monitor serum phosphate at least twice a week until return to normal range.
	
If serum phosphate level is > 10 mg/dL for 1 week following phosphate-binding therapy and low phosphate diet, hold/delay Pemigatinib.
 
If there is recurrence of serum phosphate level in this range following 2 dose reductions, permanently discontinue Pemigatinib.
	
Restart Pemigatinib at reduced dose with phosphate binders when serum phosphate is < 7 mg/dL.

------------	---	--	--

\*\* The following describe actions above:

- Hold/Delay = Treatment can be made up (see Section 8.3) as part of this cycle;
- Discontinue = Treatment is totally stopped.

8.3 For reasons that are consistent with the Dose Modifications outlined above in Section 8.2, Pemigatinib treatment that is held/delayed for purpose of adverse event management can be “made up” within a given cycle:

- The scheduled duration of a cycle is 21 days (3 weeks).
- For purpose of accommodating an established Pemigatinib dose hold/delay, the number of days in any given cycle may be increased up to 14 total days, in order to accommodate a maximum cycle length of 35 days (5 weeks).

Note: The purpose of this guidance is not to accommodate re-dosing in the absence of an established Pemigatinib dose hold/delay. For example, inadvertently missed or vomited doses of Pemigatinib are not to be “made up” within the cycle, but rather should be omitted from the cycle (and noted as such in the patient-completed medication diary).

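### Two stop rules in 8.2 count two dose reductions although a patient never raised to 18 mg has only one, and the repeat Cycle 1 labs that 1.5 requires after up-titration are missing from 4.1

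*Combined protocol and SAP*

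**What the plan says.** **Dose levels.** Section 8.1 lists 18 mg (level 1), 13.5 mg (level 0) and 9 mg (level -1). "All patients are scheduled to initiate Pemigatinib at Dose Level 0", which is 13.5 mg. Section 7.1 allows 18 mg from Cycle 2 only if phosphate never passed 5.5 mg/dL in Cycle 1, the patient is compliant, and no related adverse event of Grade 2 or higher is ongoing. Section 7.2 keeps everyone else at 13.5 mg and permits a later increase on the same criteria. Section 1.5 sets the floor: "Dose reductions below 9 mg are not allowed". It gives the count of two for one group only: "For participants who are up-titrated from 13.5 mg to 18 mg, a maximum of 2 dose level reductions is also recommended".

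**Stop rules.** Two discontinuation rules in 8.2 count reductions. One covers "Any recurrent Grade 3 toxicity after 2 dose reductions", with the rider "Exceptions require written approval of sponsor-investigator". The other, in the row for phosphate above 10 mg/dL, stops treatment permanently "If there is recurrence of serum phosphate level in this range following 2 dose reductions" and has no exception route. Other rows call for a restart at a lower dose, for example "If serum phosphate level recurs at > 7 mg/dL, restart Pemigatinib" at a reduced dose.

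**Assessments after up-titration.** Section 1.5 says that patients raised to 18 mg have to agree to the whole set of Cycle 1 assessments, naming PK, hematology and chemistry. Section 4.1 schedules hematology and chemistry on Days 1, 8 and 15 of Cycle 1, and from Cycle 2 on Day 1 only. It has no PK row, and the blood table in 14.1 lists no PK sample. No footnote to 4.1 and nothing in 7.1 or 7.2 carries the requirement.

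**The concern.** The first problem is that the trigger count does not fit the dose ladder. What is at stake is patient safety and consistent handling across sites. Section 1.5 supports continuous dosing partly by saying that the adjustment criteria are clear in the protocol. For a patient who went from 13.5 to 9 mg they are not.

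The misfit is sharpest for phosphate. A patient above 5.5 mg/dL in Cycle 1 fails the criterion for 18 mg, and 7.2 reuses that criterion as written. The patients who are hyperphosphatemic from the start therefore have no scheduled route to two reductions, and so none to the phosphate stop rule.

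The second problem is a requirement in the rationale that never reaches the schedule sites work from. Section 1.5 delays up-titration so that phosphate and adverse events can be watched for a cycle, and its simulation predicts phosphate above 5.5 mg/dL at 18 mg. Yet 4.1 plans no phosphate test between the increase and the next Day 1. The twice-weekly monitoring in 8.2 begins only once a value above 7 mg/dL has been found.

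**Working it through.** **Reductions available.** Count the levels in 8.1 below the patient's highest dose, with the floor at 9 mg.

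| Highest dose | Levels below it | Reductions available | Required by both rules |
|---|---|---|---|
| 18 mg | 13.5, 9 | 2 | 2 |
| 13.5 mg | 9 | 1 | 2 |

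The first row reproduces the figure in 1.5 for up-titrated patients. The second shows that the triggers cannot be met by anyone who stays at 13.5 mg, with two exceptions: re-escalation after discussion (8.3), or a later increase (7.2), could supply a second step down. The floor sentence in 1.5 stands in the paragraph on up-titrated patients, but 8.1 offers no level below 9 mg to anyone.

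**What 8.2 and 8.3 tell a site about a patient already at 9 mg.**

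- Still workable: holds; same-dose restart for unrelated AST/ALT/ALP or other Grade 3 events, for Grade 3 ANC without fever or infection, for Grade 2 platelets, for Grade 4 neutropenia that resolves in 7 days or less, and after a first hold for phosphate above 7 and up to 10 mg/dL; permanent stop for "Any other Grade 4 toxicity, if clinically significant"; removal after a delay of more than 42 days.
- Not workable, because no lower dose exists: restart after related AST, ALT or ALP above 5 x ULN; related Grade 4 ANC that lasts longer, febrile or infected Grade 3 ANC, or platelets below 50; other related Grade 3 toxicity; recurrent phosphate above 7 mg/dL; phosphate above 10 mg/dL.
- Cannot trigger: the two count-based stop rules.

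**Two readings follow.** Strictly, the patient is held, there is no permitted dose to restart at, holds are capped at 14 days per cycle, and removal follows after more than 42 days. Alternatively, a site takes 9 mg as the lowest available dose and restarts there once the event resolves. If the event then recurs, the stop rule meant for recurrence does not apply. The text does not choose between these readings.

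**Labs in the first 18 mg cycle.** Cycle 1 days {1, 8, 15} less the Cycle 2+ day {1} leave Days 8 and 15 unscheduled. Scheduled chemistry is 7 days apart in Cycle 1. After the increase (18 / 13.5 = 1.33 times the dose) the next scheduled test is 21 days later, or 21 + 3 = 24 days with the visit window.

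**Effect of the reworded trigger.** A trigger defined as recurrence at 9 mg fires after two reductions from 18 mg, as now, and after one from 13.5 mg.

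**The case against.** The strongest reply to the first problem is that the text already fails safe. For a related Grade 3 event, or phosphate above 10 mg/dL that meets the hold criterion, the only restart offered is at a lower dose. None exists at 9 mg, so the patient stays off drug. The 14-day cap in 8.3 covers every hold, so it matters little that the phosphate row states no limit of its own. The phosphate table is also headed as a recommendation. Much of this stands and limits the risk. It does not remove the gap, because stopping has to be inferred and a site could as reasonably restart at 9 mg.

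The reply to the second is that 1.5 is part of the protocol, that 4.1 omits its requirement without contradicting it, and that exceeding 5.5 mg/dL is the aim of the increase. That is fair, but a site that follows 4.1 will still miss the tests that 1.5 requires.

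A reader might infer that the gap is common. Table 13 shows hyperphosphataemia in 4 of 8 patients on continuous and 8 of 13 on interval dosing at 9 mg, together 12 of 21 (57%). That counts values above 5.5 mg/dL, and up to 7 mg/dL 8.2 asks only for diet, so it says nothing about the rule for values above 10. The 14 of 16 with hyperphosphataemia on 13.5 mg continuous dosing suggest that many patients may not qualify for 18 mg. They do not show how many would be reduced to 9 mg and then have a further event. Section 1.4 points the other way: among 106 monotherapy patients, only pneumonia, dehydration and small intestinal obstruction led to discontinuation in more than one patient, so hyperphosphatemia did so in at most one.

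**Conclusion.** Both inconsistencies are real and should be fixed. In (a), the rules ask for two reductions where the ladder from 13.5 mg gives one, so they cannot trigger for a never-escalated patient unless re-escalation or a later increase intervenes. The practical risk is moderate. The documents do not support reading this as patients at 9 mg left without protection: holds, the other-Grade-4 rule and the 42-day removal still apply. They give no rate for reduction to 9 mg, or for further related Grade 3 toxicity or phosphate above 10 mg/dL there, so the frequency cannot be estimated.

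In (b), following 4.1 as written leaves 21 to 24 days without a scheduled phosphate test after a one-third dose increase. Day 1 labs do continue in every cycle; what is missing is Days 8 and 15, and PK throughout.

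Neither part bears on the primary test. The two-stage rule in 16.21 counts responses, and alpha, power and sample size are unaffected.

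**What to change.** **(a)** In both rules, replace the count of two reductions with *at the lowest permitted dose (9 mg)*, and extend the written-approval exception of the Grade 3 rule to the phosphate rule. If a sentence is added for first, non-recurrent related events at 9 mg that call for a lower dose, it should say two things. The recurrent Grade 3 rule takes precedence, including for AST/ALT, ANC and platelets. Restart at 9 mg needs written approval of the sponsor-investigator; otherwise treatment is discontinued. Without these conditions such a sentence would overlap the stop rule and loosen the present text. The cost is that a few patients at 9 mg would stop earlier unless an exception is approved.

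**(b)** Add a footnote to 4.1, cross-referenced in 7.1 and 7.2: *In the first cycle at 18 mg, hematology and serum chemistries (including phosphate) are also required on Day 8 and Day 15 (±3 days).* Delete the PK mention in 1.5, or schedule PK in 4.1 and 14.1 if it is intended. The cost is two blood draws per up-titrated patient, at most 24 x 2 = 48. The documents do not say how many patients will be raised. Table 13 counts hyperphosphataemia at any time, whereas the criterion for 18 mg looks at Cycle 1 only and adds compliance and toxicity conditions, so a smaller central estimate is not supported.

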## 9.0 Ancillary Treatment/Supportive Care

## 9.1 Prohibited Medications

### 9.11 The following medications and measures are PROHIBITED:

- Concomitant administration of potent CYP3A4 inhibitors and inducers and moderate CYP3A4 inducers. Based on the low overall bioavailability of topical ketoconazole, there are no restrictions on topical ketoconazole. See appendix II for a list of potent CYP3A4 inhibitors and inducers.
- Any concomitant use of a selective FGFR inhibitor (other than Pemigatinib).
- Investigational study drug for any indication.
- Use of any anticancer medications (other than Pemigatinib).

## Restricted and Cautionary Medications

- 9.12 The use of mild or moderate CYP3A4 inhibitors or inducers should involve careful monitoring.
- 9.13 The pH level of stomach acid impacts the absorption of Pemigatinib. As a result, *limited use* of proton pump inhibitors or antacids while on study is recommended.
- 9.14 Calcium-based phosphate binding medications while on study should be avoided or, if medically necessary and unavoidable, used with caution due to a concern for soft tissue mineralization.

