potent CYP3A4 inducer, rifampin (decrease pemigatinib AUC by 85%). A PBPK model was developed and validated using in vitro and clinical DDI data. PBPK model-simulated pemigatinib AUCs were increased by approximately 50% for moderate CYP3A4 inhibitors and decreased by more than 50% for moderate CYP3A4 inducers. In addition, PBPK modeling shows no DDI effect when pemigatinib was coadministered with a weak CYP3A4 inhibitor or inducer.

[figure not shown]

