3.2 Registration – Exclusion Criteria

3.21 Prior treatment with Pemigatinib.

3.22 Prior treatment with a selective FGFR inhibitor  $\leq$  180 days (6 months) prior to registration.

3.23 Known hypersensitivity or severe reaction to an FGFR inhibitor, or to the excipients of Pemigatinib (i.e. microcrystalline cellulose, sodium starch glycolate, and magnesium stearate).

3.24 Current evidence of clinically significant corneal or retinal disorder confirmed by ophthalmologic examination.

3.25 Treatment with other investigational study drug for any indication for any reason, or receipt of anticancer medications  $\leq$  14 days prior to registration.

3.26 Major surgery  $\leq$  28 days prior to registration.

3.27 External beam radiation therapy  $\leq$  28 days prior to registration, or palliative radiation for non-CNS disease  $\leq$  14 days prior to registration.

3.28 Brain metastases, central nervous system (CNS) metastases, leptomeningeal disease, or spinal cord compression

NOTE: Patients who are asymptomatic or previously treated and stable, without evidence of progression for  $\geq$  28 days prior to registration are eligible

NOTE: Patients taking concomitant corticosteroids and/or anticonvulsants are allowed if patient is on a stable or decreasing dose of such treatment for  $\geq$  28 days prior to registration.

3.29 History or presence of significant cardiovascular disease or condition including:

- Uncontrolled angina pectoris (Canadian Cardiovascular Society Grade II-IV despite medical therapy).
- Congestive heart failure (New York Heart Association Class III or IV).
- Uncontrolled arrhythmia requiring therapy. Note: Patients with a pacemaker and well-controlled rhythm for  $\geq$  28 days prior to registration are not excluded.
- Any of the following occurring  $\leq$  6 months prior to registration: Myocardial infarction, angioplasty, cardiac stenting, coronary/peripheral artery bypass graft, cerebrovascular accident or transient ischemic attack.

3.29a Failure to adequately recover (i.e. to  $\leq$  Grade 1(according to CTCAE v.5) or to pre-treatment baseline) from adverse events (AEs) deemed by the investigator as clinically significant and attributed to prior therapy.  
Exception: alopecia.

3.29b Current use of prohibited medication as described in Section 9.11.

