3.29c Use of any potent CYP3A4 inhibitors or inducers or moderate CYP3A4 inducers (see Appendix II)  $\leq$ 14 days or 5 half-lives (whichever is shorter) prior to registration. Note: Topical ketoconazole will be allowed.

3.29d History of hypovitaminosis D requiring supraphysiologic doses to replenish the deficiency. Note: Patients receiving vitamin D food supplements are allowed.

3.29e History and/or current evidence of ectopic mineralization/calcification, including but not limited to soft tissue, kidneys, intestine, myocardia, or lung; with the exception of calcified lymph nodes and asymptomatic arterial or cartilage/tendon calcification.

3.29f Unable or unwilling to swallow Pemigatinib and keep a medication diary, or significant gastrointestinal disorder(s) that could interfere with absorption, metabolism or excretion of Pemigatinib per the discretion of the investigator.

3.29g Any of the following because this study involves an investigational agent whose genotoxic, mutagenic and teratogenic effects on the developing fetus and newborn are unknown:

- Pregnant women.
- Nursing women.
- Women of childbearing potential or men able to father children who have a female partner of childbearing potential, who are unwilling to employ acceptable contraception as outlined in Appendix I.

3.29h Known history of human immunodeficiency (HIV) infection or positivity on immunoassay confirmed per local standards

Note: HIV test is not required for screening, but patients with a known history of HIV infection will be excluded.

3.29i Evidence of active hepatitis B (HBV) or hepatitis C (HCV) infection

3.29j Other known active malignancy  $\leq$  5 years prior to registration.

**EXCEPTIONS:** Non-melanotic skin cancer or carcinoma in situ of the cervix, provided there is no known active disease and no additional therapy for the condition is ongoing or required during the trial period

**NOTE:** Anti-estrogen/androgen therapy or bisphosphonates allowed.

3.29k Co-morbid systemic illness, other severe concurrent disease, or psychiatric illness/social situation which, in the judgment of the investigator, would make the patient inappropriate for entry into this study, limit compliance with study requirements, or interfere significantly with the proper assessment of safety and

toxicity of the prescribed regimen.

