**Notes:**

R Research funded (see Section 19).

1. If the subject is participating through the COLOMATE platform: The COLOMATE Companion Trial Recommendation Form must indicate that the patient has met molecular eligibility to screen. The patient must be registered to the companion study ≤30 days from date of COLOMATE Companion Trial Recommendation Form completion. If the COLOMATE Companion Trial Recommendation Form recommends a different companion study, patient may still enroll after approval by the study PI or designee. Form must be uploaded to supporting documentation folder in RAVE.

2. Vital Signs: Including heart rate, blood pressure and temperature (oral or tympanic) and ideally performed with subject in a recumbent or semirecumbent position after 5 minutes of rest.
3. Prohibited Medications: List of prohibited medications in section 9.11 should be reviewed at study entry and during treatment.
4. Comprehensive Eye Examination: To be performed by a qualified ophthalmologist at screening, once every 3 cycles starting with Cycle 3, Day 1 ( $\pm 14$  days); at EOT, and as clinically indicated. The eye examination should include a visual acuity test, slit-lamp examination, OCT, and funduscopy with digital imaging. Additional assessments should be performed if clinically relevant retinal findings are observed on ophthalmologic exams and in participants with reported visual AEs or change in visual acuity, if the events or changes are suspected to be of retinal origin. Every effort should be made to ensure that all subsequent examinations are performed by the same ophthalmologist.
5. Computed Tomography (CT) / Magnetic Resonance Imaging (MRI): Baseline evaluation of disease status by CT or MRI completed  $\leq 28$  days prior to registration. Baseline and subsequent scans to include imaging of the primary site of disease plus any additional sites of known or suspected disease. Re-scanning to occur every 9 weeks (minus 1-6 days) after initiating protocol treatment on Cycle 1, Day 1. (The minus 1-6 day scan window is intended for flexibility in scheduling re-scans during Week 3 of every 3rd cycle – i.e. re-scanning intended between Days 15-21 of Cycles 3, 6, 9, etc.)  

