15.16 **Potential Drug Interactions:** The data from Study INCB 54828-104 demonstrated a clinically significant effect on pemigatinib exposure when a potent CYP3A4 inhibitor (itraconazole) or inducer (rifampin) is coadministered, and physiologically based pharmacokinetic modeling showed that coadministration of a moderate CYP3A4 inducer decreased the pemigatinib AUC by at least 50%. In addition, the data from Study INCB 54828-106 demonstrated a modest effect on the overall exposure of pemigatinib following coadministration of the gastric pH-modifying agents esomeprazole and ranitidine. Therefore, pemigatinib can be dosed without respect to concomitant use of PPIs or H2 antagonists. In vitro transport studies indicated that pemigatinib is a substrate of both P-gp and BCRP, but it is unlikely that efflux by these 2 transporters plays an important role in the oral absorption of pemigatinib. Pemigatinib is an inhibitor of P-gp, OCT2, and MATE1. However, at the proposed therapeutic dose, physiologically based pharmacokinetic

modeling showed that a clinical drug-drug interaction is unlikely to occur as a result of pemigatinib-mediated inhibition of these transporters.

Refer to the study Protocols for details regarding restricted and prohibited concomitant medications.

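### Section 9.12 puts moderate CYP3A4 inducers under careful monitoring, although 9.11 prohibits them and the protocol's modelling has them at least halving pemigatinib exposure

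*Combined protocol and SAP*

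**What the plan says.** Section 9.11 lists what is prohibited on study, and its first item is: "Concomitant administration of potent CYP3A4 inhibitors and inducers and moderate CYP3A4 inducers". It then directs the reader onward: "See appendix II for a list of potent CYP3A4 inhibitors and inducers".

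Section 9.12, under the heading for restricted and cautionary medications, says: "The use of mild or moderate CYP3A4 inhibitors or inducers should involve careful monitoring".

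Three other places deal with the same drugs:

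- Exclusion 3.29b: "Current use of prohibited medication as described in Section 9.11".
- Exclusion 3.29c: "Use of any potent CYP3A4 inhibitors or inducers or moderate CYP3A4 inducers (see Appendix II"), within 14 days or 5 half-lives before registration, whichever is shorter.
- Section 4.1, note 3: "List of prohibited medications in section 9.11 should be reviewed at study entry and during treatment".

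The protocol reports the modelled effect twice. Section 1.5 has pemigatinib AUC "decreased by more than 50% for moderate CYP3A4 inducers". Section 15.16 says that "coadministration of a moderate CYP3A4 inducer decreased the pemigatinib AUC by at least 50" percent. Section 1.5 also reports no interaction with weak inhibitors or inducers, and an AUC rise of about 50% with moderate inhibitors.

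**The concern.** Two adjacent rules give different instructions for one drug class. A site that meets a moderate inducer during treatment can find it prohibited in 9.11 and subject only to monitoring in 9.12. Section 9.12 names no monitoring parameter and no dose action.

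The exclusions deal with drugs in use at entry. The exposed case is a drug started later. Section 9.22 provides for antibiotics and for treatment of newly diagnosed conditions, and Appendix II classes nafcillin (an antibiotic) and telotristat ethyl (an antidiarrheal) as moderate inducers.

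Two things are at stake for such a patient. The first is under-exposure to the study drug. The second is the titration rule in Section 7.1. A patient whose phosphate never exceeds 5.5 mg/dL in Cycle 1, who is compliant and who has no ongoing Grade 2 or higher treatment-related event goes to 18 mg. Section 1.5 reads a missed target as a sign of low exposure at 13.5 mg. With an inducer on board, the missed target may reflect the interaction and not the patient's own exposure. None of the three criteria asks about interacting drugs.

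A smaller slip adds to this. The pointer in 9.11 sends staff to Appendix II for potent agents only, although the appendix also has a list headed for moderate inducers, with 17 entries.

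**Working it through.** **Step 1: does 9.12 cover moderate inducers?** There are two ways to read it. If the words mild or moderate govern both nouns, moderate inducers are covered. If they govern only inhibitors, inducers of every strength are covered, which conflicts with 9.11 even more. No reading leaves moderate inducers out.

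**Step 2: which classes conflict?**

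| Class named in 9.12 | Status in 9.11 | Modelled effect on AUC (1.5, 15.16) | Consistent? |
|---|---|---|---|
| Mild inhibitors | not prohibited | none | yes |
| Mild inducers | not prohibited | none | yes |
| Moderate inhibitors | not prohibited | rise of about 50% | yes |
| Moderate inducers | prohibited | fall of 50% or more | **no** |

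Only one of the four classes conflicts. In 9.12 it shares a rule with classes that show no modelled effect.

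**Step 3: which sentence is wrong?** Exclusion 3.29b and note 3 in Section 4.1 both name 9.11 as the operative list. Exclusion 3.29c names moderate inducers directly. The modelling supports prohibition. Nothing supports 9.12 for this class.

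**Step 4: size of the exposure loss.** The AUC figure is the output of a physiologically based model whose inputs are not in the documents, so it cannot be recomputed. The two places that report it agree.

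Inputs:

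- fractional fall in AUC, f ≥ 0.50 (Sections 1.5 and 15.16)
- linear pharmacokinetics over the doses studied (Section 1.6)
- doses of 18, 13.5 and 9 mg, with 9 mg the lowest permitted (Sections 1.5 and 8.1)

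Formula: equivalent dose = dose × (1 − f) ≤ dose × 0.50.

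- 18 mg: 18 × 0.50 = 9 mg at most
- 13.5 mg: 13.5 × 0.50 = 6.75 mg at most
- 9 mg: 9 × 0.50 = 4.5 mg at most

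These are upper bounds, because the stated fall is a minimum.

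**Step 5: what that means for target inhibition.** Section 1.6 gives observed trough inhibition of pFGFR2 of 82% at 13.5 mg and 64% at 9 mg. Since 6.75 mg is below 9 mg, a patient on 13.5 mg with a moderate inducer would be expected to fall below 64%. This assumes that inhibition rises with exposure and that the trough falls at least in proportion to AUC. The effect is reduced, not absent.

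**Step 6: the phosphate trigger.** In the continuous-dosing columns of Table 13, hyperphosphatemia was reported in 14 of 16 patients at 13.5 mg (87.5%) and 4 of 8 at 9 mg (50.0%). The groups are small, but the direction is what the titration argument needs: lower exposure makes the target harder to reach.

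No sample-size, power or type I error figure enters this point.

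**The case against.** The strongest reply is that this is a drafting overlap with little practical reach. Section 9.12 does not say in terms that moderate inducers are allowed, while 9.11 prohibits them by name. A site that follows the stricter rule complies with both. The schedule in Section 4.1 also marks a prohibited-medication review at screening, on Days 1, 8 and 15 of Cycle 1, on Day 1 of each later cycle, at end of treatment and at safety follow-up. Section 9.22 is general supportive-care text and does not authorise a prohibited drug. All of this is fair, and it limits how many patients could be affected. It does not remove the conflict: a site relying on 9.12 would have written support, and whether that use was a deviation would be open to argument.

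The titration argument is narrow. It applies only if the inducer is taken in Cycle 1 and stops the patient ever passing 5.5 mg/dL. Raising the dose of an under-exposed patient also serves the stated aim of raising concentration, whatever the cause. Both points stand. What remains is that the signal would be misread.

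The 9 mg step is the lowest dose-reduction level and is not presented as an efficacy threshold, so falling below it does not by itself show lost benefit. Carrying an AUC loss over to trough inhibition is a further assumption. Both are accepted as limits on Steps 4 and 5.

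On the pointer, 3.29c already sends readers to Appendix II for moderate inducers, and the inhibitor table there, as it appears in the document text, is not graded by potency. The pointer is therefore the lesser point, and its new wording should not promise a grading that the table lacks.

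**Conclusion.** The concern holds. Section 9.12 contradicts 9.11 for moderate CYP3A4 inducers, and 9.12 is the sentence in error. It governs conduct during treatment, so it should be corrected, although it does not threaten the validity of the design.

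For a patient treated under 9.12, exposure would be at most half of that intended: 13.5 mg would act like at most 6.75 mg, and 18 mg like at most 9 mg. This rests on the modelled AUC fall and on linear pharmacokinetics, both as stated in the protocol. The expectation of trough inhibition below 64%, against 82% at 13.5 mg, rests on the extra assumptions in Step 5.

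The documents give no frequency of inducer use. The number affected is unknown, and it may be 0 if sites enforce 9.11. No loss of response rate or power is claimed. No safety harm from 18 mg is claimed either, since that dose is planned and phosphate is monitored.

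**What to change.** Make two wording changes:

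1. Reword 9.12 along these lines: *Mild CYP3A4 inhibitors, mild CYP3A4 inducers and moderate CYP3A4 inhibitors may be used with careful monitoring. Moderate CYP3A4 inducers are prohibited (see 9.11).*
2. Reword the pointer in 9.11 along these lines: *Appendix II gives examples of CYP3A4 inhibitors and lists potent and moderate CYP3A4 inducers.* If the inhibitor table in the appendix is indeed ungraded, say so there, so that staff check potency in the reference the appendix already names.

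The prohibition in 9.11 and exclusions 3.29b and 3.29c stay as they are. The cost is two sentences in a protocol amendment and a notice to sites. Design, data collection and sample size do not change.
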